10. RECRUITMENT

Six SYHealth community health centers across San Diego County have been selected based on their serving predominantly Latinx and AA client population and having the Zip codes with the highest number of COVID-19 cases in the County. These clinics are located in National City, Logan Heights, Lincoln Park, Valencia Park and San Ysidro. Each clinic will be randomly selected and randomized evenly to either the intervention or control conditions, using computer-generated randomization plans prepared using SAS statistical software under the direction of the lead study statistician. Clinic-level randomization was selected to minimize between-arm contamination of intervention and control conditions. Participants from both intervention (n=500) and control sites (n=500) will be recruited using reactive recruitment, including the use of community partner social media platforms, and flyers distributed in the SYH target health centers and high traffic, readily visible areas, where eligible participants are likely to see them (e.g., grocery stores, local CBO's, parks, barber shop, cafés, food banks, gyms, local restaurants). Flyers will include study information and contact information for study staff. Likewise, the project staff publicized the rapid vaccine effort (e.g., mini-vaccination stations) by posting flyers that noted locations, dates, and times of vaccine distribution, and through presentations about the project at community meetings. Project staffing, training, and support, including the selection of nurses and outreach staff (e.g., peer-health educators and research assistants) with complementary research skills and personal knowledge of the community will be key to the success of the project. Two bilingual Latinx (one male and one female) and two AA (one male and one female) outreach workers trained in research ethics and protocols, and familiar with this population will approach individuals who appear to be eligible (Latinx and AA adults ages 16 years or older) at the SYH community centers and mini-vaccination stations in the participating communities, confirm eligibility, and describe the study to those eligible. Research staff will update time logs and continuously update our sampling frame until recruitment is finalized. The reason for refusal or ineligibility will be recorded. Extensive efforts will be made to have an equal representation of Latinx and Black community members and at least 40% women.

Additionally, two separate FGs (one in English and one in Spanish) will be conducted (n=2; 8-10 participants per group) following the implementation of *2VIDA!* with members of the Latinx and AA community in San Diego to understand the socio-structural barriers to COVID-19 information and resources (e.g., testing) and vaccine uptake (e.g., medical mistrust, discrimination, stigma, transportation, access to vaccination site, lack of insurance) as well as acceptability of the *2VIDA!* intervention. Participants will be recruited from six SYH community health centers (from both intervention and control sites) that are located in the communities with the highest cases of COVID-19. Participants will be recruited using selective sampling, a non-probability sample that is selected based on characteristics of a population and the aims of the proposed research and is acceptable for the proposed qualitative research.²² The research assistants will recruit Latinx and AA adults by two mechanisms: 1) from the waiting room of the community health centers (both control and intervention sites) and when they come to the clinic or mini-vaccination site to complete their 2nd dose of the vaccine and if interested in participating scheduling an appointment for them to come into the community health center to learn more about the study. We will use a standard recruitment script and research assistants will confirm eligibility with potential study participants via verbal assessment of the following inclusion criteria: 1) identify as Latinx or African American, 2) 16 years of age or older, 3) reside in one of the target communities (National City, Lincoln Park, Logan Heights, Valencia Park, San Ysidro), 4) literate in English or Spanish, 5) able to provide written and informed consent (including permission to record FG session). We will recruit equal number of Latinx and AA participants for each session, as well as equal number of individuals who both have and haven't received the vaccine as part of *2VIDA!* to provide an in-depth discussion and have a better understanding of the community needs. Each FG will take place in the private conference room located in the clinics, will follow a semi-structured open-ended guide, last between 60-90 minutes and be facilitated by a moderator ([name]) and note-taker (who also records each session). This data will allow us to identify structural barriers, acceptability and feasibility of *2VIDA!* on COVID-19 vaccination uptake.

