Acceptance and uptake of COVID-19 vaccines will be instrumental to ending the pandemic, however, public confidence in vaccination is fragile, especially among racial and ethnic minorities. A recent nationally representative longitudinal study found that the public's likelihood of getting a COVID-19 vaccine declined from 74% in early April to 56% in early December 2020, despite the press releases in November 2020 of a high vaccine efficacy for 2 vaccines in phase 3 trials and the surge in cases during this timeframe.¹⁴ Likewise, self-reported likelihood of getting COVID-19 vaccination was lower among women, AA individuals, and those with lower educational backgrounds. Similarly, other studies have indicated that Latinx are less likely to trust the vaccine and that there is skepticism among Latinx communities across the country¹⁵ due to unequal access to health care, the lack of reliable information (especially in Spanish), coupled with disinformation.¹⁶ These findings highlight the mistrust between racial and ethnic minorities and public health officials, likely due to historical racism in health care and implicit bias.⁵ This is concerning due to their disproportionately higher burden from COVID-19 disease and because high levels of vaccination are necessary to reach herd immunity and control the pandemic. These findings emphasize the need for interventions that address these barriers and rebuilt trust in our communities of color. The proposed study is significant in that it will conduct extensive individual and community level awareness, education, outreach and health promotion that center on providing COVID-19 medically accurate and culturally competent information (in English and Spanish at 8th grade level) in order to empower our communities of color.

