access to COVID-19 vaccine, vaccine hesitancy). Additional measures at baseline and follow-up will be used as covariates (e.g., outreach and health communication, vaccine hesitancy or mistrust). Mean differences, both within and between treatment and control groups as well as group by treatment interaction effects will be analyzed. The targeted sample size is sufficient to detect a small effect size (.20) with power = .90 at alpha = .05 accounting for moderate participant attrition.

Descriptive Statistics. To describe the overall sample regarding demographics, structural and individual barriers, and potential covariates of intervention effects at baseline, prevalence statistics and means and standard deviation will be provided for all baseline variables; Cronbach's alpha of .70 will be required to be considered reliable. **Baseline Analyses to Detect Differences Between Treatment Groups.** Chi-square analyses and paired t-tests will be used to detect differences in demographics, knowledge of COVID-19 vaccine, access to COVID-19 vaccine, acceptance of COVID-19 vaccine and series completion, COVID-19 resource-seeking behaviors and linkage into care between intervention and control groups. Demographic variables included in these analyses will be age, gender, race/ethnicity, education, household income, marital status, and having insurance. Those variables differing across treatment groups at the $p < .20$ level will be included in subsequent adjusted outcome analyses. For the qualitative data analysis, final translated electronic transcripts will be imported into Dedoose. Analysis will be done through identification of recurrent themes following Crabtree and Miller's 5 step "interpretive process."¹⁹ First, transcripts will be read to identify common themes, codes will be developed and ~10% of data will be double coded and inter-rate reliability assessed. Coded text will be extracted and organized and read to identify emergent themes.⁶⁵ Matrices will be created to compare codes by themes (e.g., medical mistrust, discrimination, stigma, transportation, access to vaccination site, lack of insurance). Data will be utilized to refine *2VIDA!*, assess acceptability, and inform future vaccination efforts among underserved communities.

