*Please note that only one community health center out of their 25 clinics is currently delivering *2VIDA!* as a clinical program and all of their clinics are offering the vaccine on site (no mini-vaccination stations). For the purposes of this research we will randomize 6 community health centers and their surrounding communities that are predominantly Latinx and AA to receive either *2VIDA!* or the standard of care for vaccine delivery (i.e. no components of *2VIDA!* will be deployed). In order to avoid contamination, the community health center where the *2VIDA!* was developed (e.g., Chula Vista) and is currently being implemented as a clinical program will be excluded from this study.

9. HUMAN SUBJECTS (2 paragraphs maximum)

Human subjects will be involved according to the study design and data collection activities detailed in Aims 1-3. All data collection will proceed under the direction of [name] from UCSD and [name] from SYH in accordance with the current standards of human subjects research taking place in SYH community health centers as outlined in state of California law. Additionally, [name] will oversee all analyses and protection of subjects in coordination with [name] and members of the CBPR working group. [name] (Co-Investigator and licensed physician) from SYH will oversee implementation of the COVID-19 vaccine based on the U.S. Food and Drug Administration (FDA) and Centers for Disease Control and Prevention (CDC) recommendations and guidelines.^{1,7}

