17. RISK/BENEFIT ASSESSMENT

Based on previous research and efforts towards the COVID-19 vaccine development and subsequent FDA Emergency Use Authorization, we know that there is a demonstrated benefit of receiving the COVID-19 vaccine and addressing vaccine hesitancy among racial/ethnic minorities that have been severely impacted by the pandemic is critical. Health benefits are hypothesized and determining this is the purpose of the research study. Study participants will receive COVID-19 Individual Awareness & Education, COVID-19 Community Outreach & Health Promotion, COVID-19 Individual Health Education & Linkages to Medical and Supportive Services and provision of COVID-19 vaccine at participating SYH community centers and mini-vaccination stations in the communities where they live. Due to the severity of COVID-19, the high rates of infection and deaths among AA and Latinx communities and the current low uptake of the vaccine (only 14% of Latinx and 3% of AA have received at least one dose of a coronavirus vaccine compared to 60% of White individual)^{10,11} we believe that the 2VIDA! intervention is promising and the AA and Latinx communities will benefit in receiving the intervention – which centers on providing medical education and increasing access to the vaccine.

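### Protocol section 10 does not say whether its Latinx/Black and women targets apply overall, per arm or per clinic, and the 3:3 clinic randomisation is not balanced on race/ethnicity, so the targets can be met with unequal arms.

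*Protocol*

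**What the plan says.** **Composition.** Protocol section 10 (Recruitment) states: "Extensive efforts will be made to have an equal representation of Latinx and Black community members and at least 40% women". The sentence names no level (arm, clinic or total), and it is a best-efforts aim, not a quota. For the focus groups, by contrast, sections 8 and 10 ask for equal numbers of Latinx and AA participants in each session.

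**Allocation.** Section 10: "Each clinic will be randomly selected and randomized evenly to either the intervention or control conditions". The note closing section 8 says "we will randomize 6 community health centers and their surrounding communities that are predominantly Latinx and AA". No stratification, matching or constraint is described. On enrolment, section 10 says "Participants from both intervention (n=500) and control sites (n=500) will be recruited using reactive recruitment".

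**Prognostic relevance.** Section 17 reports that "only 14% of Latinx and 3% of AA have received at least one dose of a coronavirus vaccine". Section 6 reports that "self-reported likelihood of getting COVID-19 vaccination was lower among women, AA individuals, and those with lower educational backgrounds", without giving sizes for these subgroups.

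**Adjustment.** Section 8 (Data Analysis) lists the variables to be compared between arms at baseline: "Demographic variables included in these analyses will be age, gender, race/ethnicity, education, household income, marital status, and having insurance". Any that differ at p < .20 enter the adjusted outcome analyses. The SAP has the same rule and also lists gender and race/ethnicity.

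**The concern.** With six clinics in different communities, randomisation gives little protection against arms of different racial/ethnic make-up. The recruitment target is the one place where the plan tries to shape composition. Because its level is unstated, staff could meet it on the total while the arms diverge.

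Divergence need not come from the clinic draw alone. Participants are approached after clinics are allocated, and the mini-vaccination stations exist only at intervention sites, so the two arms recruit partly through different channels.

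If uptake differs between the groups, unequal arms create or hide a difference in vaccine receipt and series completion before any intervention effect. The analysis must then repair by modelling what recruitment could have limited.

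**Working it through.** **1. The plan's own figure.** The protocol and SAP call the sample "sufficient to detect a small effect size (.20) with power = .90 at alpha = .05 accounting for moderate participant attrition". Taking .20 as a standardised mean difference with 500 per arm, two-sided, no attrition and no clustering: .20 × √(500/2) = 3.162, and 3.162 − 1.960 = 1.202, so power is .885. That is close to .90. The plan gives neither the metric of the effect size nor the sidedness nor the attrition rate.

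**2. Unadjusted gap with no intervention effect.** Inputs: 500 per arm (section 10), 50:50 overall, and uptake of 14% Latinx and 3% AA (section 17, illustration only). The mixes are assumptions, because the documents give no clinic compositions.

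Uptake in an arm = s × .14 + (1 − s) × .03, where s is the Latinx share. For 70:30 v 30:70: .7 × .14 + .3 × .03 = .107, and .3 × .14 + .7 × .03 = .063. The gap is .044. Cohen's h = 2·asin√.107 − 2·asin√.063 = .16.

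| Latinx:AA by arm | Uptake | Gap (points) | h | Chance that an unadjusted test is significant in that direction |
|---|---|---|---|---|
| 60:40 v 40:60 | 9.6% v 7.4% | 2.2 | .08 | 24% |
| 70:30 v 30:70 | 10.7% v 6.3% | 4.4 | .16 | 70% |
| 80:20 v 20:80 | 11.8% v 5.2% | 6.6 | .24 | 96% |

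In general, gap = (difference in group uptake) × (difference in Latinx share). At 70:30 v 30:70, an assumed 5-point group difference gives 5 × .4 = 2 points and an assumed 20-point difference gives 20 × .4 = 8 points.

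**3. How likely such splits are.** There are 20 ways to split six clinics 3:3. With equal clinic sizes and the 14%/3% rates:
- Assumed clinic Latinx shares of 10, 20, 40, 60, 80 and 90%: 12 of 20 allocations differ by at least 20 points, and the unadjusted two-sided type I error averages 32%.
- Assumed shares of 30, 40, 45, 55, 60 and 70%: 2 of 20 differ by at least 20 points, and the average is 11.5%.

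**4. What the p < .20 rule does.** With 500 per arm it flags a 55% v 45% imbalance 97% of the time and a 20-point imbalance almost always. The largest imbalance that escapes it is about 1.2816 × √(.25 × 2/500) = .041, or 4.1 points. At an 11-point group difference that is worth .0405 × 11 = 0.45 points of uptake.

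**5. What the adjustment costs.** With equal arms and 50:50 overall, the correlation between arm and group equals the difference in shares. Under simple linear adjustment the variance of the arm effect is inflated by 1/(1 − r²), before any gain from explaining outcome variation.
- 70:30: r = .4, 1/(1 − .16) = 1.19. Effective n = 500/1.19 = 420 per arm, and power for .20 falls from .885 to about .83.
- 80:20: r = .6, 1/(1 − .36) = 1.56. Effective n = 320 per arm, power about .72.

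These figures ignore attrition and clustering.

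**6. Women.** 20% in one arm and 60% in the other average (20 + 60)/2 = 40%, so that target too can be met with very unequal arms. No outcome rates by sex are given, so no gap is calculated.

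**The case against.** The strongest reply is that the plan already deals with this. Race/ethnicity and gender are on the baseline comparison list in both documents, and step 4 shows that any material imbalance would trigger adjustment. That stands. A reader might infer that imbalance alone could pass for an intervention effect in the trial's result; the documents do not support this, because the gaps in step 2 belong to an unadjusted comparison and adjusted analyses are planned.

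A reader might also infer that adjustment must fail for want of overlap. At 70:30 v 30:70 each arm still holds at least .3 × 500 = 150 people from each group, and at 80:20 it holds 100. Overlap becomes thin only if clinics are close to segregated, and nothing in the documents shows that. Section 10 says all six were chosen because they serve mainly Latinx and AA clients.

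The inputs are soft as well. The 14% and 3% are early background coverage, not expected rates among people recruited at clinics and vaccination stations. Section 6 describes mistrust in both communities and does not compare Latinx with AA people directly. Reading .20 as Cohen's h is only one option.

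Finally, steering recruitment after open allocation gives staff discretion over whom they approach, which carries its own selection risk. That is a good reason for a soft target and against a fixed 250/250 quota.

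The objection does not restore the precision lost to adjustment. Nor does it answer the greater dependence on the model where race/ethnicity tracks clinic, with three clinics per arm and no cluster-level analysis described.

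**Conclusion.** The point holds as a gap in specification that is worth closing. The level of the composition target is unstated and the clinic randomisation is not balanced on race/ethnicity, so the target as written does not prevent unequal arms.

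Under the illustrative 14% v 3%, the unadjusted gap is 2.2 to 6.6 points across splits from 60:40 to 80:20. The planned adjustment would remove most of it, provided group is recorded and modelled properly. What remains is a variance inflation of 1.19 to 1.56 for splits from 70:30 to 80:20, before clustering, and heavier reliance on the model. The size depends on clinic compositions and a group difference in uptake that the documents do not supply.

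Two further inferences go too far. The text does not say that the targets apply to the whole sample; it is silent, and because the same section describes recruitment by arm, a per-arm reading is equally open. Nor does it imply bias in a known direction: chance imbalance from randomising six clinics can fall either way.

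**What to change.** In section 10, state that the targets apply within each arm as soft targets: about half Latinx and half AA, and a similar share of women, at least 40%, in each arm. Tally both by arm from the existing recruitment log, and use the same approach procedure in both arms. State how people who identify as both Latinx and AA are counted, since eligibility allows both.

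As a complement, state in section 8 and in the SAP that race/ethnicity and sex enter the outcome models regardless of the baseline p-value. The p < .20 screen can stay for the other variables.

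If the target is met in each arm, the race-driven gap is zero and the precision cost in step 5 disappears.

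**Cost.** A few sentences and a regular tally from a log that is already kept. Recruitment may slow for the harder-to-reach group in one arm, and effort directed to that group must not turn into selective approach by staff who know the allocation.

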11. COMPENSATION FOR PARTICIPATION

When this work was first submitted, working group members decided that providing a reimbursement for completing the survey may not be well received in our target communities given they will complete at the same time they receive the COVID-19 vaccine, and this could be misinterpreted as being paid to receive the vaccine and would be morally flawed. This decision was made based on community leaders and CBO's recommendations. However, since then many organizations including the local government now offer an incentive for receiving the vaccine. Therefore, we propose to provide participants with a \$20 VISA gift card for completing the baseline survey and an additional \$20 VISA gift card for completing the follow-up survey (4-weeks). For those individuals who already completed a baseline and follow-up survey prior to the approval of this amendment, we propose to send them a link (similar to the You Call the Shot program) for a \$40 VISA gift card participating in the study.

Participants from the focus groups (n=2; 8-10 participants per group) will be compensated via \$20 VISA gift cards for their time and transportation. Working group members decided that providing a reimbursement for participating in the focus groups would be acceptable as it will be done at a separate time from when they are offered the COVID-19 vaccine.

12. INFORMED CONSENT

At recruitment, research assistants will confirm eligibility with potential study participants via verbal assessment of the following inclusion criteria: 1) age 16 years or older; 2) identify as Latinx and/or AA; 3) biologically male or female; 4) be a resident of one of the three communities selected for the intervention (National City, Lincoln Park, Logan Heights, Valencia Park or San Ysidro); 5) literate in English or Spanish; 6) no known history of severe allergic reactions to any components of the vaccine; 7) no history of immune disease; 8) not be pregnant; 9) no plans to move from the area in the following 30 days; 10) able to provide voluntary informed consent; and 11) able to provide complete contact information for themselves and two additional contact individuals (for follow-up 2nd vaccine shot). These data will be recorded in the form of a Client Recruitment Log. Although pregnancy is not a contraindication for COVID-19 vaccination, working group members decided that vaccination of pregnant women may not be well received in our target communities. This decision was also made based on community leaders and CBO's recommendations. Research assistants will record data regarding eligibility and reasons for non-participation where applicable. We are requesting a waiver of parental consent for subjects enrolled in the study who are ages 16-17. We request that minors who are 16-17 are able to provide assent for themselves as this study poses minimal risk to the subjects. The biggest risk is the loss of confidentiality and appropriate measures will be taken by the research personnel to ensure all data is kept confidential. These include assigning a unique study ID to each participant, only sharing data with approved research personnel, and keeping all data on a password protected device.

However, parental consent will be requested by our community partners (SYH) before they apply the vaccine. Furthermore, participants who refer low digital literacy levels and/or limited access to internet or digital technologies will be informed about the option to conduct the follow-up survey via Computer Assisted Telephone Interviewing (CATI) or videoconferencing and screen sharing (VCSS). Those agreeing to participate will be escorted to a private room within the participating SYH community centers or in their cars or tents (if they come by foot) at the mini-vaccination stations and will provide informed digital consent (e.g., tablet) and complete the survey via a tablet (self-administered). We will set-up mini-vaccination stations in the parking of three public parks in the selected intervention sites and tent-lined lanes for eligible recipients to drive up. Participants will be inside their car and wearing a mask at all times during the consent process. Inside their car they will complete the 10-15 min. survey, receive the COVID-19 vaccine, and pull aside for a 15-minute observation period. We will also set-up additional tents with portable chairs at least 6 feet apart for participants who do not own a vehicle and want to receive the vaccine at the mini-stations. Although the mini-vaccinations will be in open public spaces (e.g., local park) because the set-up between the vaccine stations will be at least 6 feet apart, we expect this will allow for privacy for those that come by foot or do not own a vehicle. However, those participants who feel uncomfortable will be invited to the health center to complete the consent process and survey in a private room. All participants will be assigned a unique identifier to link initial survey and follow-up survey (when they receive the 2nd dose). The baseline survey will take approximately 20 minutes and the follow-up survey last 10 minutes, both will be self-administered (tablet). The research staff will be available in case the participants don't understand a question or need help with any aspect of the survey. Following survey completion, participants will be eligible to receive the COVID-19 vaccine if they provided written informed consent. Although participants would have already been screened for eligibility, the research assistants will confirm again that they do not have any known history of severe allergic reactions to any components of the vaccine, no history of immune disease, and not be pregnant. Further, SYH staff will have parents to provide consent for their children (16–17-year-old) to receive the vaccine. Registered nurses from SYH will proceed to apply the COVID-19 vaccine and as previously mentioned, will observe the participant has no reaction for 15 minutes. SYH will follow strict vaccination protocols (based on the U.S. Food and Drug Administration⁷ and Centers for Disease Control and Prevention recommendations and guidelines)¹ and will report all vaccine administration errors, all serious adverse events, cases of Multisystem Inflammatory Syndrome (MIS), and cases of COVID-19 that result in hospitalization or death following administration of the COVID-19 Vaccine to the IRB and to the Vaccine Adverse Event Reporting System (VAERS). The same procedure will be followed for the 2nd dose of the vaccine. Additionally, a detailed protocol has been developed by SYH for this intervention to handle adverse events, although none have occurred so far in the application of the COVID-19 vaccine to front line healthcare providers. Staff members have assigned specific responsibilities (e.g., if warranted, nurses will administer epinephrine or Benadryl and maintain an airway; outreach workers would call 911 and wait for the ambulance). The medical director of the study on behalf of SYH, [name] who is a licensed physician, will be on call at all times, and a licensed nurse will manage all aspects of the COVID-19 vaccination phase.

As previously mentioned, two separate FGs (one in English and one in Spanish) will be conducted (n=2; 8-10 participants per group) following the implementation of *2VIDA!* with members of the Latinx and AA community in San Diego to understand the socio-structural barriers to COVID-19 information and resources (e.g., testing) and vaccine uptake (e.g., medical mistrust, discrimination, stigma, transportation, access to vaccination site, lack of insurance) as well as acceptability of the *2VIDA!* intervention. Participants will be recruited using selective sampling, a non-probability sample that is selected based on characteristics of a population and the aims of the proposed research and is acceptable for the proposed qualitative research.²⁰ Research assistants will confirm eligibility with potential study participants via verbal assessment of the following inclusion criteria: 1) identify as Latinx or African American, 2) 16 years of age or older, 3) reside in one of the target communities (National City, Lincoln Park, Logan Heights, Valencia Park, San Ysidro), 4) literate in English or Spanish, 5) able to provide written and informed consent (including permission to record FG session). The written paper consent process for the focus groups will be conducted by UCSD staff the day of the FG prior to beginning the session. Each FG will take place in the private conference room located in the clinics, will follow a semi-structured open-ended guide, last between 60-90 minutes and be facilitated by a moderator ([name]) and note-taker (who also records each session). This data will allow us to identify structural barriers, acceptability, and feasibility of *2VIDA!* on COVID-19 vaccination uptake.

